**Table 12: Precision of Binomial Confidence Intervals** 

N	95% CI			
20	27-73			
40	34-66			

For each of the primary immunogenicity objectives, a power analysis is provided below for testing the following hypotheses with the planned sample size, where  $p_c$  = probability of response in comparator arm; where  $p_e$  = probability of response in experimental arm.

## Test for difference in proportion responders:

 $H_0$ :  $p_c - p_e = 0$  – No difference in response probabilities

 $H_1$ :  $p_c - p_e \neq 0$  – difference in response probabilities

Table 13 illustrates the minimum detectable differences in the probability of responding (e.g., attaining seroconversion or  $NF_{50} \ge 0.56$  [seroprotection]) between participants who receive AV7909 as the lyophilized formulation or liquid formulation using a two-sided likelihood ratio test with 80% power and alpha = 0.05. It is assumed that up to 10% of subjects (N=2) will be excluded from the per-protocol analysis in each group. Seroconversion rates of 10% to 60% are considered.

Table 13: Minimum Detectable Difference in the Probability of Response with 80% Power

Re	Probability of Response in	80% Power					
	Comparator Group A	Minimal Detectable Difference	Probability of Response in Experimental Group B				
	0.10	0.39	0.49				
	0.20	0.43	0.63				
N = 18	0.30	0.43	0.73				
	0.40	0.42	0.82				
	0.50	0.39	0.89				
	0.60	0.35	0.95				

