## **5.2** Treatment Assignment Procedures

#### **5.2.1** Enrollment and Randomization Procedures

Per ICH E6 GCP, screening records will be kept at the participating VTEU site to document the reason why an individual was screened, but failed trial entry criteria. The reasons why individuals failed screening will be recorded in the Statistical and Data Coordinating Center's (SDCC) Advantage eClinicalSM (Electronic Data Capture System).

Once consented and upon entry of demographic data and confirmation of eligibility for this trial, the participant will be enrolled in the electronic data capture system. The participant will be enrolled and randomly assigned with equal allocation (1:1) to 1 of 2 treatment groups, stratified by age category (18-30 years old and 31-45 years old) and by gender.

Enrollment of participants will be done online using the enrollment module of Advantage eClinicalSM. The randomization code will be prepared by statisticians at the SDCC and included in the enrollment module for this trial. Advantage eClinicalSM will assign each participant to a treatment arm after the demographic and eligibility data have been entered into the system. A designated individual at the VTEU site will be provided with a code list for emergency unblinding purposes, which will be kept in a secure place.

Instructions for use of the enrollment module are included in the Advantage eClinicalSM User's Guide. Manual back-up procedures and instructions are provided for use in the event that the participating VTEU site temporarily loses access to the internet or the online enrollment system is unavailable.

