### 7.2.2 Special Assays or Procedures

### Serological/Immunogenicity Assays

Serum will be collected for toxin neutralization assay (TNA) and reported as ED50 and NF50 and collected for anti-PA IgG concentration by ELISA and reported as µg/mL. Blood samples (sera) for determination of TNA titers and anti-PA IgG will be collected on the days outlined in the Schedule of Events in Appendix A. Specific procedures related to collection, processing, storage, and shipment of the samples are provided in the Manual of Procedures.

The TNA assay being used in this trial has been validated by Battelle Memorial Institute (Columbus, Ohio) under National Institute of Allergy and Infectious Diseases sponsorship {Clement, 2008}. The assay measures the functional ability of antisera containing anti-PA antibodies to specifically protect cells against *B. anthracis* lethal toxin cytotoxicity {Stinson et al, 2005; Li et al., 2008}. The TNA assay results will be reported as the reciprocal of a serum sample dilution that results in 50% neutralization of lethal toxin cytotoxicity (50% effective dilution; ED50). To standardize assay results, the results are divided by the ED50 of a serum reference standard, and the resulting ratio is reported as a 50% neutralization factor, NF50. Reference standard AVR801 will be used.

The method of quantitative anti-PA IgG ELISA has been described previously (Semenova VA, Schiffer J, Steward-Clark E, Soroka S, Schmidt DS, Brawner MM, Lyde F, Thompson R, Brown N, Foster L, Fox S, Patel N, Freeman AE, Quinn CP J Immunol Methods. 2012 Feb 28; 376(1-2):97-107).

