#### 11.2 Study Hypotheses

This Phase I study is not designed to test a formal null hypothesis. Rather, it is intended to obtain sufficient data to obtain meaningful estimates of the immune response induced by either vaccine formulation, and to uncover any safety issues that occur at a sufficiently high rate that they might be observed in a study of this size. The sample size facilitates formal testing of selected hypotheses as discussed in Section 11.4.3, along with the probability of observing safety outcomes and the precision of immunogenicity outcomes.

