## 11.4.3 Sample Size

While this study is not designed to test any specific null hypothesis, the following illustrates the precision and power that are available for select estimates and comparisons of interest, based on the planned sample size of N=20 participants per study arm.

Table 11 indicates the probability of observing one or more safety events, such as solicited injection site or systemic reactogenicity events or an unsolicited AE of a particular type, for a single treatment arm (N=20), and for all enrolled subjects (N=40).

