# 5. SAMPLE SIZE CONSIDERATIONS

This study is planned to enroll a total of 40 subjects, with 20 subjects in each study arm. This phase I study is not designed to test a formal null hypothesis. Rather, it is intended to obtain sufficient data to obtain meaningful estimates of the immune response induced by either vaccine formulation and to uncover any safety issues that occur at a sufficiently high rate that they might be observed in a study of this size. As such, the type one error rate, alpha = 0.05, is not adjusted for multiple comparisons. While this study is not designed to test any specific null hypothesis, the following tables illustrate the precision and power that is available for select estimates and comparisons of interest.

Table 2 indicates the probability of observing one or more safety events, such as solicited injection site or systemic reactogenicity events or an unsolicited AE of a particular type, for a single treatment arm (N=20), and for all enrolled subjects (N=40).

Binomial confidence intervals (CI) are widest (have the least precision) when the response rate is 50%. Table 3 is presented to indicate the worst-case scenario for precision of observed exact (Clopper-Pearson) binomial confidence intervals.

For each of the primary immunogenicity objectives, a power analysis is provided below for testing the following hypotheses with the planned sample size, where  $p_c =$  probability of response in comparator arm; where  $p_c =$  probability of response in experimental arm.

Test for difference in proportion responders:

 $H_0: p_c - p_e = 0$ ; No difference in response probabilities

H1:  $p_c - p_e \neq 0$ ; difference in response probabilities

Table 4 illustrates the minimum detectable differences in the probability of responding (e.g., attaining seroconversion or  $NF_{50} \ge 0.56$  [seroprotection]) between participants who receive AV7909 as the lyophilized formulation or liquid formulation using a two-sided likelihood ratio test with 80% power and alpha = 0.05. It is assumed that up to 10% of subjects (N=2) will be excluded from the per-protocol analysis in each group. Seroconversion rates of 10% to 60% are considered.

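### The only between-formulation immunogenicity comparison is framed on dichotomized responders, and no lyophilized/liquid contrast on the continuous titer is planned

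*Protocol*

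**What the plan says.** Protocol 11.2 disclaims a formal null hypothesis but adds: "The sample size facilitates formal testing of selected hypotheses as discussed in Section 11.4.3". The only immunogenicity hypothesis in 11.4.3 is equality of the response probabilities in the two arms. Its power table is introduced with "Table 13 illustrates the minimum detectable differences in the probability of responding (e.g., attaining seroconversion or" NF50 at or above 0.56, and is computed "using a two-sided likelihood ratio test with 80% power and alpha = 0.05". SAP section 5 carries the same hypothesis and table: "Table 4 illustrates the minimum detectable differences in the probability of responding (e.g., attaining seroconversion or" NF50 at or above 0.56. A responder is therefore someone whose assay value passes a cut, either a 4-fold rise or the 0.56 threshold.

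The assays themselves are continuous. Protocol 7.2.2 describes TNA as an ED50 divided by that of a reference serum, and "the resulting ratio is reported as a 50% neutralization factor"; anti-PA IgG is a concentration in µg/mL. SAP section 8 summarizes all three by arm and visit as GMT or GMC and geometric mean fold rise with t-based 95% CIs. SAP 8.2 adds reverse cumulative distribution curves and GMT/GMC plots by arm. Neither Protocol 11.6.3 nor SAP section 8 plans a between-arm contrast for immunogenicity on any scale. The secondary objective (Protocol Table 1, SAP 3.1.2) is an initial estimate of how the two formulations compare.

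**The concern.** The objective is comparative, but the plan delivers two separate columns of summaries and one illustration of what a comparison could detect. That illustration uses the coarser scale. Cutting a titer at a threshold discards how far each value lies from the cut, and at visits where nearly everyone or nearly no one passes it, little information remains. Table 13 covers comparator rates of 10% to 60% only, and shows only a higher rate in the experimental arm.

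What is at stake is how the trial is read. Detectable differences of 0.35 to 0.43 suggest that only a very large change in immunogenicity could be seen with 18 per arm. If the continuous values behave as assumed below, the same samples can show a smaller change. Without a prespecified ratio and interval, the comparison that the objective asks for is left to readers or to post hoc choice.

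**Working it through.** **Inputs from the documents.** Protocol 11.4.3 works "based on the planned sample size of N=20 participants per study arm", and "It is assumed that up to 10% of subjects (N=2) will be excluded from the per-protocol analysis in each group", so n = 18 per arm. Allocation is 1:1 (Protocol 5.2.1), alpha is 0.05 two-sided, and the six pairs of rates come from Table 13.

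**Assumption, not in the documents.** Log titer is normal with the same SD in both arms and differs only by a shift. Neither document gives an SD or a distribution.

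**Step 1: reproduce Table 13.** Sum the two binomial(18) distributions over all outcomes where the likelihood ratio statistic exceeds 3.841. This gives the third column below, 79–81%, so the plan's figure reproduces. The test is somewhat liberal: its exact size is 6.3–8.4% at true rates of 0.1 to 0.9. Fisher's exact test would have only 63–69% power on the same rows.

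**Step 2: convert each row to a shift.** d = Φ⁻¹(pe) − Φ⁻¹(pc). For 0.30 against 0.73, d = 0.613 + 0.524 = 1.137 SD.

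**Step 3: power on the log scale.** The t-test uses a noncentral t with 34 df and noncentrality d√(n/2) = 3d. For d = 1.137 this is 3.41 against a critical value of 2.032, giving 91%. The Wilcoxon column is simulated.

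| Comparator | Experimental | Responder LR test | d (SD) | t-test on log titer | Wilcoxon |
|---|---|---|---|---|---|
| 0.10 | 0.49 | 80% | 1.26 | 96% | 94% |
| 0.20 | 0.63 | 81% | 1.17 | 93% | 91% |
| 0.30 | 0.73 | 80% | 1.14 | 91% | about 90% |
| 0.40 | 0.82 | 80% | 1.17 | 93% | 91% |
| 0.50 | 0.89 | 79% | 1.23 | 95% | 93% |
| 0.60 | 0.95 | 81% | 1.39 | 98% | 97% |

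**Step 4: detectable shift at 80% power.** The t-test needs d = 0.96. Applied to the six comparator rates, that equals responder differences of 0.27, 0.35, 0.37, 0.36, 0.33 and 0.29, against 0.39, 0.43, 0.43, 0.42, 0.39 and 0.35 in Table 13. At 0.96 SD the Wilcoxon test has about 77% power; it needs about 0.99 SD.

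**Step 5: precision.** The CI half-width for a difference in mean log titer is t(0.975, 34) × √(2/18) = 2.032 × 0.333 = 0.68 SD. For assumed log10 SDs of 0.3 and 0.6, the GMT ratio is known to within a factor of 10^(0.677 × 0.3) = 1.60 and 10^(0.677 × 0.6) = 2.55. The t-test detectable ratios are 10^(0.961 × 0.3) = 1.94 and 10^(0.961 × 0.6) = 3.77.

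**Step 6: vary the assumption.**
- Values below the NF50 LLOQ set to half the LLOQ, log10 SD 0.3–0.8: about 90–98%.
- Logistic instead of normal log titers: 84–98%.
- Experimental-to-comparator SD ratio 0.67 or 1.5, Table 13 rates held fixed: t-test 79–99.9%; Wilcoxon about 77–81% in some rows.
- SD ratio 0.5 or 2: t-test 55–100%, with the low end at the 0.60 row for ratio 0.5 (55%) and the 0.10 row for ratio 2 (62%); Wilcoxon about 51–59% in the worst rows.

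**The case against.** The strongest reply is that nothing planned is weakened. The trial disclaims a formal null hypothesis (Protocol 11.2, SAP 6.8), and Protocol 11.4.3 only illustrates what an already chosen 20 per arm can do. The likelihood ratio test appears in that illustration and nowhere in the immunogenicity analysis. This stands. A reader of Table 13 might infer that the trial will run an inefficient test, or that its sample size rests on one. The documents support neither.

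Second, the continuous scale is not thrown away. Per-arm GMT/GMC and fold rise with CIs, distribution curves with both arms in each panel, and individual listings are all planned, and they largely answer the worry about visits where almost all or almost none respond. This also stands. What they do not supply is the comparison itself as a stated estimate with an interval.

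Third, the responder scale has a purpose. Protocol 2.3.1 calls NF50 of 0.56 or more a putative correlate of protection, and responder proportions are two of the three secondary outcomes. Showing detectable differences for them is legitimate, and a mean-titer comparison answers a different question. This is a reason to keep the responder table and add to it, not to replace it.

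Fourth, the gain is not assured. A reader might take the table above as showing an advantage in every row as a property of this trial. Step 6 shows otherwise: with unequal SDs the advantage disappears in some rows and reverses in others.

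**Conclusion.** The point holds as a gap in the planned comparison. The only between-formulation immunogenicity comparison described is on dichotomized responders, and no contrast on the continuous titer is planned, although the objective is comparative and the per-arm summaries needed for it are already produced.

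Under normal log titers with equal SD, effects that give the responder test about 80% power give a log-scale comparison about 90–98% at 18 per arm. The detectable effect falls from responder differences of 0.35–0.43 to the equivalent of 0.27–0.37. These figures rest on that model, since the documents give no assay SD, and markedly different SDs can remove or reverse the gain. The point does not show that any confirmatory conclusion is at risk, that 20 per arm is wrong, or that responder proportions should be dropped.

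**What to change.** 1. In SAP section 8, and to match in Protocol 11.6.3, add the lyophilized/liquid GMT ratio (NF50, ED50) and GMC ratio (anti-PA IgG) with a 95% CI at each visit. Where many values are below the LLOQ, add a rank-based comparison. Label all of this as estimation without multiplicity control, consistent with SAP 6.8.
2. In Protocol 11.4.3 and SAP section 5, place beside the responder table the log-scale precision at 18 per arm: CI half-width 0.68 SD of log titer, and detectable shift 0.96 SD for the t-test and about 0.99 SD for the Wilcoxon test. Express these as GMT ratios over a stated range of assumed SDs, and name the equal-SD assumption.
3. Keep seroconversion and seroprotection as descriptive proportions with their exact CIs.

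The cost is protocol and SAP wording, some added table rows and a little programming. No participants, visits or blood draws are added. The downside is that the precision figures depend on an assumed SD range.

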### Table 4: Minimum Detectable Difference in the Probability of Response with 80% Power

Assumed Proportion of Responders in	lers in 80% Power (N = 18)							
Comparator Group A	Minimal Detectable Difference	Probability of Response in Experimental Group B						
0.10	0.39	0.49						
0.20	0.43	0.63						
0.30	0.43	0.73						
0.40	0.42	0.82						
0.50	0.39	0.89						
0.60	0.35	0.95						

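### Protocol Table 13 and SAP Table 4 pair 80% power with alpha = 0.05, but at 18 per arm the stated likelihood ratio test has an exact type I error of 6.2% to 8.5% for response rates of 0.10 to 0.90

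*Protocol*

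**What the plan says.** Protocol 11.4.3 sets out a two-sided test of equal response probabilities in the two arms and tabulates the difference detectable for six comparator rates. The calculation is described as "using a two-sided likelihood ratio test with 80% power and alpha = 0.05", and SAP Section 5 repeats that wording for its Table 4. The sample size starts from 20 per arm ("based on the planned sample size of N=20 participants per study arm") and is reduced to 18: "It is assumed that up to 10% of subjects (N=2) will be excluded from the per-protocol analysis in each group".

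The SAP describes the error rate without qualification: "the type one error rate, alpha = 0.05, is not adjusted for multiple comparisons". Neither document says that the 0.05 is nominal or asymptotic, and neither gives the level actually achieved at 18 per arm.

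Both documents say the study is not designed around a formal null hypothesis and that these tables are illustrative. Protocol 11.2 nevertheless adds: "The sample size facilitates formal testing of selected hypotheses as discussed in Section 11.4.3".

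**The concern.** A likelihood ratio test for two proportions takes its 5% cut-off from the chi-square distribution, which is a large-sample approximation. With 18 per arm the outcome is discrete and the approximation is poor, particularly near 0 and 1, so the rule may reject a true null hypothesis more often than 5% of the time. Any excess raises the apparent power as well, so the 80% would be obtained partly by spending more than the stated error.

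A reader who takes the tables at face value, for instance when planning a larger comparison of the two formulations, would believe that these differences can be detected with 80% power while holding 5% error.

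**Working it through.** **Inputs**

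- 18 analysed per arm: 20 planned less 2 excluded (Protocol 11.4.3).
- 1:1 allocation (Protocol 5.2.1).
- Two-sided likelihood ratio test, alpha 0.05, power 80% (Protocol 11.4.3, SAP Section 5).
- Comparator rates 0.10 to 0.60 ("Seroconversion rates of 10% to 60% are considered").
- Assumed: independent binomial responses and the standard cut-off, chi-square with 1 degree of freedom, 3.8415.

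**Test statistic.** With x and y responders out of n = 18 in each arm, and e = (x + y)/2:

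G = 2[x ln(x/e) + y ln(y/e) + (n − x) ln((n − x)/(n − e)) + (n − y) ln((n − y)/(n − e))], with 0·ln 0 = 0. Reject if G > 3.8415.

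**Power and size.** There are 19 × 19 = 361 possible outcomes, and b(x; 18, p) denotes the binomial probability.

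- Power(p, q) = Σ b(x; 18, p) b(y; 18, q), summed over the rejected outcomes.
- Size(p) = Power(p, p).

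**Step 1: reproduce the table.** Solving Power = 0.80 gives all six stated differences after rounding.

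| Comparator rate | Stated difference | Recomputed difference | Power at the stated pair |
|---|---|---|---|
| 0.10 | 0.39 | 0.388 | 80.3% |
| 0.20 | 0.43 | 0.426 | 80.7% |
| 0.30 | 0.43 | 0.431 | 79.9% |
| 0.40 | 0.42 | 0.4225 | 79.5% |
| 0.50 | 0.39 | 0.393 | 79.2% |
| 0.60 | 0.35 | 0.347 | 81.1% |

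The large-sample (noncentral chi-square) power formula for the same test gives 0.417, 0.452, 0.457, 0.442, 0.410 and 0.363, which do not match. The tabled differences therefore correspond to exact binomial power with an asymptotic cut-off.

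**Step 2: exact size of the same rule.**

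| Common response rate | Exact type I error |
|---|---|
| 0.05 or 0.95 | 4.6% |
| 0.10 or 0.90 | 8.4% |
| 0.15 or 0.85 | 7.6% |
| 0.20 or 0.80 | 6.8% |
| 0.25 or 0.75 | 6.5% |
| 0.30 or 0.70 | 6.3% |
| 0.35 or 0.65 | 6.2% |
| 0.50 | 6.6% (6.55%) |

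Between 0.10 and 0.90 the minimum is 6.18% (near 0.35 and 0.65) and the maximum 8.48% (near 0.106 and 0.894). The size crosses 5% at a rate of 0.0527 and, by symmetry, at 0.9473.

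The peak near 0.10 and 0.90 comes largely from sparse outcomes. For 0 against 3 responders, G = 2[3 ln(3/1.5) + 18 ln(18/16.5) + 15 ln(15/16.5)] = 4.43, so the rule rejects. Fisher's exact p-value for the same outcome is 0.23.

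**Step 3: what a test that holds 5% achieves.** Boschloo's test uses Fisher's p-value as its statistic, with the cut-off set so that the size stays within 5% for every common rate. Here that means rejecting at Fisher p ≤ 0.0877, with a maximum size of 4.77%.

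| Comparator rate | Boschloo power at the stated pair | Boschloo 80% difference | Increase over the recomputed difference |
|---|---|---|---|
| 0.10 | 76.0% | 0.411 | 0.023 |
| 0.20 | 75.4% | 0.456 | 0.030 |
| 0.30 | 71.8% | 0.466 | 0.036 |
| 0.40 | 75.1% | 0.439 | 0.017 |
| 0.50 | 75.1% | 0.407 | 0.014 |
| 0.60 | 74.5% | 0.365 | 0.018 |

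The loss in power is 4 to 8 percentage points. Keeping the likelihood ratio statistic and raising its cut-off to hold 5% (G ≥ 4.66, maximum size 4.74%) gives power of 75.1%, 72.1%, 69.3%, 71.6%, 73.7% and 76.8%.

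**The case against.** - **No tabled number is wrong for the named test.** Alpha quoted beside a likelihood ratio test is commonly read as nominal, and the documents say exact where they mean it, as for the Clopper-Pearson intervals. The SAP sentence on the type one error rate is about multiplicity. This stands in part: it makes the defect one of labelling. It does not remove it, because the tabled power is exact and nothing tells the reader that the alpha beside it is not.
- **The table is illustrative and no planned inference uses the rule.** SAP Section 8 plans per-arm estimates with confidence intervals only. The one between-arm test mentioned as possible, for solicited symptoms in Protocol 11.6.2, is chi-square or Fisher. This stands and limits the consequence. Protocol 11.2 still points to this section for formal testing.
- **The 8.5% is a peak.** At the average of the two rates in each row the size is 6.3%, 6.3%, 6.6%, 6.3%, 6.3% and 6.6%. This is correct. The inflation near the tabled alternatives is about 1.3 to 1.6 points.
- **Boschloo is not in the plan and is itself somewhat conservative.** Its size at those row averages is 4.0% to 4.7%, so part of the power loss is its own. This also stands, and there is no single correct replacement figure. Both 5% rules examined nevertheless fall short of 80% in every row.
- **Another rule fits the table.** An unpooled Wald rule also rounds to all six values, with a size of 3.4% to 6.6% over 0.10 to 0.90. The documents name the likelihood ratio test, so that is the rule to judge.

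**Conclusion.** The concern holds. The combination of 5% type I error and 80% power is not a property of this design over rates of 0.10 to 0.90. The rule behind the tables has an error of 6.2% to 8.5% there, up to 1.7 times the stated level (8.48/5). Boschloo's test, which holds 5%, has 72% to 76% power at the same pairs.

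The practical effect is modest. Detectable differences move from 0.35–0.43 to 0.36–0.47, and in either case only very large differences between formulations are detectable. No trial conclusion depends on the rule.

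The result assumes 18 analysed per arm, independent binomial outcomes and the chi-square cut-off. If all 20 per arm were analysed, the likelihood ratio rule's size over 0.10 to 0.90 would be 4.3% to 8.5%, so the excess does not depend on the assumed exclusions.

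**What to change.** Either change is sufficient, provided it is made in both documents.

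- **(a) Label the alpha.** Keep the test and the two tables. State in Protocol 11.4.3 and SAP Section 5 that 0.05 is the nominal level of an asymptotic test, and that with 18 per arm its exact type I error is 6.2% to 8.5% for common response rates of 0.10 to 0.90. The cost is one clause in each document.
- **(b) Restate the tables with an exact test that holds 5%.** With Boschloo's test the 80% power differences for comparator rates 0.10 to 0.60 are 0.41, 0.46, 0.47, 0.44, 0.41 and 0.36 (the last is 0.3647 before rounding). The cost is two table edits and the name of the test. The stated differences become 0.01 to 0.04 larger.

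Option (a) is the cheaper and is enough for an illustrative table. Neither option changes the sample size, data collection or any planned analysis.
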